## Sites

For SAE Forms completed by someone other than the Investigator, the Investigator will be required to countersign the original SAE form to confirm agreement with the causality and severity assessments. The form should then be returned to NCTU and a copy kept in the Site File. Investigators should also report SAEs to their own Trust where required by local practice.

On becoming aware that a participant has experienced an SAE, the Investigator (or delegate) must complete, date and sign a SAE form. The form should be e-mailed to NCTU using the following e-mail address:

## FOR SAE REPORTING ONLY: [contact]

## NCTU

On receipt of a SAE Form, seriousness and causality will be reviewed independently by the medical monitor responsible for determining causality assessments.

Trial	TB-DILI Trial	Protocol	1.2	date:	02-Aug-2022	Page 40 of 58
name:		version:				

# 10.4.1. Provision of follow-up information

Follow-up information should be provided on a SAE Follow-up form. Only events deemed to be related to trial treatment will be followed up to resolution or stabilisation of the event.

# 10.5. Reference Safety Information

The Reference Safety Information (RSI) will be the SmPC as described in the table below.

Drug	SmPC
Ethambutol	Ethambutol 100mg film coated tablets. Intrapharm Laboratories Limited.
Isoniazid	Isoniazid, each ampoule contains 50mg Isoniazid in 2ml of solution.
	Alliance Pharmaceuticals Limited.
Rifampicin	Rifampicin 300mg gelatin capsules. Generics [UK] Limited t/a Mylan.
Zinamide	Zinamide 500mg white tablets. Genus Pharmaceuticals Limited.

Treatment for this condition varies across clinical practice in both dosage and formulation therefore we have included the SmPC for all active drugs being used in the trial. Due to the treatment schedule, relatedness will be assessed against the appropriate SmPC(s) for the drug(s)s that the participant has been administered at the time of the event.

Any updates to the RSI will be reviewed annually in line with the Development Safety Update Report (DSUR).

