## DILI Recurrence

[Could occur at any timepoint during treatment period]

- EQ-5D-5L questionnaire
- Discontinuation of control or intervention ATT regimen

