# 10.1. Adverse Events (AEs) and reporting requirement/ procedures

The collection and reporting of AEs will be in accordance with the Medicines for Human Use Clinical Trials Regulations 2004 (and subsequent amendments).

All IMPs being used in this trial are being used within license and have well characterised safety profiles.

The treatments provided to both randomised groups are widely available within the NHS, used in standard care and considered to be safe. Expected adverse events (listed in the table below) are as per the SmPC for trial treatments. These events are secondary outcomes and will be collected as part of the eCRF. Adverse events will be coded using the Medical Dictionary for Regulatory Activities (MedDRA) as per NCTU standard practice and the number of occurrences reviewed throughout the trial by the TMG and the Data Monitoring Committee (DMC).

Body system		Adverse event							
Blood and lymp	hatic system disorders	Agranulocytosis							
		Aplastic anaemia							
		Thromb	ocytopeni	а					
		Thromb	ocytopeni	a with	purpura				
		Neutro	penia						
		Eosinop	hilia						
		Leukop							
			lytic anaen						
		Dissemi	inated intr	avascu	lar coagu	ulation			
		Vitamin	K depend	ent coa	agulation	n disorders			
Congenital, fam	ilial, and genetic disorders	Porphy	ria						
Ear and labyrint	h disorders	Deafne	SS						
		Tinnitus	5						
		Vertigo							
Endocrine disor	ders	Adrenal insufficiency							
Eye disorders		Tear discolouration							
	Optic neuritis								
		Pyrexia							
Trial TB-DI name:	LI Trial		Protocol version:	1.2	date:	02-Aug-2022	Page 37 of 58		

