# 10.3. Events that do not require reporting

Individuals who develop a DILI significant enough to require hospital admission are at high risk of developing other adverse events. To this end, anticipated events that are consequences of the underlying disease, common events in the study population, or are part of the primary and secondary outcomes will be exempt from expedited reporting. Adverse events that are not listed as expected events (table 4) and are not deemed as serious and related to trial treatment (i.e. a SUSAR) by the assessing clinician are also exempt from reporting.

A SAE judged by the Investigator or medical monitor (in this case the CI), to have a reasonable causal relationship with the trial medication will be regarded as a Serious Adverse Reaction (SAR). The medical monitor will also assess all SARs for expectedness. If the event meets the definition of a SAR that is unexpected (i.e. is not defined in the Reference Safety Information (RSI) –see Section 10.1) it will be classified as a SUSAR.

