## **10.4.** SAE reporting Procedure – NCTU trial Office

Only SAEs that are deemed related by the assessing clinician (i.e. a SUSAR) need reporting. When completing the SAE form, the Investigator will be asked to define the causality and severity of the AE. The SAE form must be sent to the NCTU as soon as possible and no later than 24 hours after first becoming aware of the event (or obtaining the follow-up information from the participant).

On receipt, NCTU will allocate each SAE a unique reference number which will be forwarded to the site as proof of receipt within 1 working day. If confirmation is not received within 1 working day, the site should contact the NCTU. The SAE reference number will be quoted on all correspondence and follow-up reports regarding the SAE and filed with the actual SAE in the Site File and TMF.

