# 10.6. Reporting period

Details of unexpected AEs (except those listed is section 10.1) will be documented and reported from the date of commencement of protocol defined treatment 12 months after randomisation. In the case where participants are still being treated at the 12-month follow-up, the reporting period will be extended to 3 months post the 12-month follow-up.

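### Section 10.5 uses the SmPC to judge relatedness and section 10.3 sends expectedness to a pooled list, so one serious event can be a SUSAR under one section and not under another

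*Protocol*

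**What the plan says.** Section 10.5 defines the reference: "The Reference Safety Information (RSI) will be the SmPC as described in the table below". That table has one SmPC for each of the four drugs. The section then adds that "relatedness will be assessed against the appropriate SmPC(s) for the drug(s)s that the participant has been administered at the time of the event".

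Section 10.3 classifies a serious reaction by expectedness, but places the reference elsewhere. An event that "is not defined in the Reference Safety Information (RSI) –see Section 10.1) it will be classified as a SUSAR". Section 10.1 holds Table 4, introduced by "Expected adverse events (listed in the table below) are as per the SmPC for trial treatments". Table 4 is arranged by body system and attributes no event to a drug or an arm. Of the same events, section 10.1 says: "These events are secondary outcomes and will be collected as part of the eCRF". Section 10.6 also uses the section 10.1 list, to exclude events from the documentation of unexpected AEs.

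The duty to report is in section 10.4: "Only SAEs that are deemed related by the assessing clinician (i.e. a SUSAR) need reporting". The reporting period in section 10.6 runs "from the date of commencement of protocol defined treatment 12 months after randomisation". At a DILI recurrence, section 9.1.4 lists "Discontinuation of control or intervention ATT regimen".

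**The concern.** Causality and expectedness are separate judgements. Causality asks whether a drug the participant received could have produced the event. Expectedness asks whether a related event is already described in the product information. The definitions table in section 10 keeps them apart: an adverse reaction may relate to any dose, and product information decides whether it is unexpected. Section 10.5 applies the product information to the first question and adds a timing phrase that can be read as dropping a drug once it has been stopped. Section 10.3 takes the second question to a different reference.

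At stake is whether a serious reaction is classed as a SUSAR and so expedited to the DMC chair, the MHRA and the REC. For some events it is also whether the trials unit hears of them at all. No efficacy estimate depends on this.

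**Working it through.** The protocol gives no figure to reproduce. The check sets its sections side by side.

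| Place | Judgement | Reference or test |
|---|---|---|
| Section 10, AR definition | Relatedness | Any dose given; no limit to current drugs |
| Section 10, UAR definition | Expectedness | Applicable product information |
| 10.3 | Causality | Trial medication; no timing limit |
| 10.3 | Expectedness | RSI, said to be in 10.1 (pooled Table 4) |
| 10.5 | Relatedness | Single-drug SmPCs, with a timing phrase |
| 10.4 | Duty to report | Related only, with related equated to SUSAR |
| 10.4 (Sites) | Duty to report | A form for an SAE, with no relatedness condition |
| 10.8.2, 10.10 | Annual report; DMC review | All SAEs |

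**Case 1: a related serious event in an EHR participant, on Table 4 only because of pyrazinamide.** Following 10.3 to 10.1, the event is listed, so it is expected and not a SUSAR. Using the SmPCs in 10.5 for ethambutol, isoniazid and rifampicin, it is not listed, so it is unexpected and a SUSAR. The two routes give opposite answers. Table 4 attributes nothing to a drug, so the protocol does not show which events these are.

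**Case 2: an unlisted serious event after a drug has been stopped.** If 10.5 means drugs currently taken, the stopped drug has no SmPC in play and the event can be read as unrelated. Under 10.4 no form is then needed. The medical monitor's independent review begins only when a form arrives, so there is no second look. The event is then missing from what 10.8.2 and 10.10 describe as all SAEs. If 10.5 means drugs given up to that time, the drug stays in play, but the SmPC is still being used for the wrong judgement.

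**Case 3: a related, expected serious event.** The first half of the 10.4 sentence requires a report. Its parenthesis, read literally, does not, because an expected reaction is not a SUSAR.

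**Length of the window.** I read 10.6 as running to 12 months, taken as 52 weeks. This ignores the few days before the first dose and the 3-month extension for participants still on treatment. The EoT questionnaire falls one week after treatment ends.

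- Control: W25 in both Figure 2 and 9.1.4, so treatment ends at about W24. 52 − 24 = 28 weeks; 28/52 = 54%.
- Intervention by 9.1.4: W37, so about W36. 52 − 36 = 16 weeks; 16/52 = 31%.
- Intervention by Figure 2: W33, so about W32. 52 − 32 = 20 weeks; 20/52 = 38%.
- Pyrazinamide in control stops at W8 in both places. 52 − 8 = 44 weeks.

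**Which drugs count after W8.** Figure 2 stops pyrazinamide and rifampicin in control and rifampicin in intervention. Section 9.1.4 stops ethambutol and pyrazinamide in control and ethambutol in intervention. On the currently-taken reading, the SmPCs in play between W8 and EoT are therefore ethambutol and isoniazid by the figure, but isoniazid and rifampicin by the text.

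**The case against.** The strongest reply is that these are two wording slips and that other sections supply the right rule. Section 10.5 speaks of drugs that have been administered, not drugs being taken, and in a sequential reintroduction this can mean drugs given so far. The AR definition and 10.3 put no time limit on causality. An investigator who worked from those alone could judge correctly. This stands as far as it goes: it shows that 10.5 is ambiguous, not that it forbids considering a stopped drug. It does not remove the conflict over where the RSI sits, which no reading resolves.

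A reader might infer several stronger points that the protocol does not support.

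- That reactions after a drug is stopped are never reported. Table 4 events are collected in the eCRF, and their numbers are reviewed by the TMG and the DMC.
- That liver failure after withdrawal would be lost. Acute hepatic failure is in Table 4, DILI recurrence and its severity are outcomes, and a blinded panel reviews possible episodes. Section 10.3 exempts outcome events from expedited reporting whatever 10.5 says.
- That EHR participants never took pyrazinamide. Section 4.1 requires a DILI on standard 4-drug treatment, so all were exposed before entry. They are only not reintroduced to it.
- That 54% or 31 to 38% measures misclassification. These are calendar shares. Section 14.2.2 takes the risk of treatment-related DILI after the drugs stop to be zero, although that says nothing of other reactions.

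**Conclusion.** The safety classification is wrong as written and should be amended. The SmPC is tied to relatedness against the protocol's own definitions, and the RSI is placed in two sections that can classify the same serious event differently. The equation of related with SUSAR in 10.3 and 10.4 turns the site's relatedness judgement into the reporting gate.

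The consequence is limited. Expedited SUSAR handling is at risk for listed events whose listing comes from a drug the participant was not given in the trial. Any report at all is at risk only for an unlisted serious event that the site judges unrelated. Listed events and DILI outcomes remain captured, and no trial estimate changes.

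The number of affected events cannot be estimated from the protocol. The 28 weeks (control) and 16 to 20 weeks (intervention) out of 52 rest on planned durations and show only how long the ambiguity about stopped drugs applies after planned treatment. Case 1 assumes that at least one Table 4 entry comes from the pyrazinamide SmPC alone, which the table does not reveal.

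**What to change.** - **10.5:** state that causality is judged against any trial drug received, whether or not stopped, taking account of time since the last dose. State that the SmPC of each drug judged causally related decides expectedness only.
- **10.3:** point to section 10.5 for the RSI. Say whether the exemption for outcome events still covers a Table 4 event that is unexpected for the drugs judged causally related.
- **10.1 and 10.6:** state that Table 4 is the eCRF collection list and is not used for expectedness.
- **10.3 and 10.4:** remove the equation of related with SUSAR. Set one SAE reporting duty that agrees with the Sites text in 10.4 and with the all-SAE wording in 10.8.2 and 10.10.
- **Figure 2 and 9.1.4:** reconcile which drugs stop at W8 and when the intervention arm's EoT falls. This point takes no view on which is right.

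The cost is a short protocol amendment and a line on the SAE form. A few more events may be classed as related or unexpected, and sites may complete more forms, depending on the duty chosen. Apart from reconciling the treatment-schedule passages, it leaves treatment, sample size and analysis unchanged.

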# 10.6. Reporting period

Details of unexpected AEs (except those listed is section 10.1) will be documented and reported from the date of commencement of protocol defined treatment 12 months after randomisation. In the case where participants are still being treated at the 12-month follow-up, the reporting period will be extended to 3 months post the 12-month follow-up.

## 10.7. Monitoring pregnancies for potential serious adverse events

The safety profile of the drugs being used are well known therefore there is no requirement to monitor pregnancies for potential SAEs.

## 10.8. Reporting to the Competent Authority and Research Ethics Committee

## 10.8.1. Suspected Unexpected Serious Adverse Reactions

On becoming aware of a SUSAR, the Trial Manager (or delegate) will notify the Sponsor as soon as possible. The Sponsor will report a minimal data set of all individual events categorised as a fatal or life threatening SUSAR to the MHRA and Research Ethics Committee (REC) within 7 days. Detailed follow-up information will be provided within an additional 8 days. All other events categorised as SUSARs will be reported within 15 days.

SUSARs will be unblinded to allow reporting to REC and the MHRA.

Trial	TB-DILI Trial	Protocol	1.2	date:	02-Aug-2022	Page 41 of 58
name:		version:				

# 10.8.2. Serious Adverse Reactions

The NCTU will report details of all SAEs and SARs (including SUSARs) to the MHRA and REC annually from the date of the Clinical Trial Authorisation, in the form of a Development Safety Update Report (DSUR).

# 10.8.3. Adverse Events

Details of all AEs will be reported to the MHRA on request.

## 10.8.4. Other safety issues identified during the course of the trial

If any urgent safety measures are taken, the CI shall immediately and in any event no later than 3 days from the date the measures are taken, give written notice to the MHRA, the relevant REC and the sponsor, of the measures taken and the circumstances giving rise to those measures.

## 10.9. Investigators

Details of all SUSARs and any other safety issue which arises during the course of the trial will be reported to Principal Investigators. A copy of any such correspondence should be filed in the Investigator Site File.

## 10.10. Data Monitoring Committee (DMC)

The independent DMC will review all SAEs.

## 10.11. Reporting to third parties

No reporting of adverse events to third parties is expected. Any safety issues identified during the course of the trial will be notified to the MHRA.

# **11.Data Handling and Record Keeping**

## 11.1. Source Data

Source data are defined as all information in original records and certified copies of original records of clinical findings, observations, or other activities in a clinical trial necessary for the reconstruction and evaluation of the trial.

In order to allow for the accurate reconstruction of the trial and clinical management of the participant, source data will be accessible and maintained.

Each site will record the location of source data at their site using a source data location log prior to commencing recruitment and signed by the Principal Investigator. For the TB-DILI trial, source data refers to, but is not limited to, the participant's medical notes, data recorded directly into the eCRF, baseline paper questionnaires and source data worksheets (when direct entry to the eCRF is not possible), and follow-up questionnaires.

All data collected directly from participants will be considered as source data within the eCRF. Where paper questionnaires are issued to participants these will be returned to the NCTU for data entry and will be considered source data. Where questionnaire data is obtained via telephone, these data will be entered directly into the eCRF or collected on paper proforma (where direct eCRF is not possible) by a member of the NCTU and will be considered source data.

Trial	TB-DILI Trial	Protocol	1.2	date:	02-Aug-2022	Page 42 of 58
name:		version:				

# 11.2. Electronic Case Report Form (eCRF) Completion

Data reported within the eCRF may comprise or will be consistent with, the source data, and any discrepancies will be investigated. Staff delegated to complete eCRFs will be trained to adhere to ICH-GCP guidelines and trial-specific guidance on the completion of the eCRF.

Where necessary, paper SAE forms will be completed by site staff and a copy scanned and emailed to NCTU for data entry.

In all cases it remains the responsibility of the site's Principal Investigator to ensure that the eCRF has been completed correctly and that the data are accurate. This will be evidenced by the electronic signature of the site's Principal Investigator on the eCRF. It is the responsibility of the Principal Investigator to ensure there are site staff in place locally to complete data entry into the eCRF in a timely manner.

# 11.3. Data Management

Details about data handling will be specified in the Data Management Plan (DMP). This will include the agreed validation specification which will validate data for consistency and integrity as it is entered.

All trial data will be entered onto the REDCap database through the eCRF with participants identified only by their unique trial number and initials The REDCap eCRF database will be developed and maintained by NCTU. Access to REDCap will be restricted and secure. Any missing or ambiguous data will be queried with the site via the eCRF. Sites should respond to data queries in a timely manner, ideally within 2 weeks of the query being raised. All access and data transactions will be logged in a full audit trail.

Data will be held on clinical trial servers. These servers are located within The University of Nottingham data centres, which are managed and monitored 24/7. Security is both physical (secure limited access) and electronic (behind firewalls, access via user accounts (user name and password)), restricted access (e.g. site users only have access to their site's data, and by user type/role). All access and data transactions will be logged in a full audit trail.

Participants' eCRF data will be reviewed and soft-locked ) on an ongoing basis once they are deemed to have a complete set of data that has passed data validation checks (i.e. there are no data queries outstanding). Once all participants' data have been soft-locked and the statistical analysis plan has been finalised, the trial database will be hard locked (set to read only). This will be done prior to the final data analysis.

## **11.4.** Archiving

It is the responsibility of the Sponsor to ensure that all documents in the Sponsor file are retained for 25 years after the end of trial. It is the responsibility of the NCTU to ensure that all documents in the TMF are retained for at least 25 years after the end of trial and that Principal Investigators ensure all essential trial documentation contained within the Investigator Site Files and participant source data worksheets at their site are securely retained for at least 25 years after the end of the trial. The end

Trial	TB-DILI Trial	Protocol	1.2	date:	02-Aug-2022	Page 43 of 58
name:		version:				

of the trial is defined in section 13. No documents will be destroyed without prior approval from the Sponsor.

The Trial Master File and trial documents held by NCTU on behalf of the sponsor shall be archived at secure archive facilities deemed appropriate for research data archive by the University of Nottingham. All trial databases and associated meta-data encryption codes will be appropriately archived and the details documented within NCTU.

Documents will be archived following any regulatory requirements and any local procedures. No documents will be destroyed without prior approval from the Sponsor.

## 11.5. Data sharing

Individual participant medical information obtained as a result of this trial is considered confidential and disclosure to third parties is prohibited with the exceptions noted in this protocol.

Participants' contact details, including name, address, telephone/mobile number and email will be shared between participating sites and NCTU for the purposes of follow up, issuing questionnaires and electronic reminders (text/email) for the trial. The University of Nottingham's approved provided of SMS texting services eSendex (https://www.esendex.co.uk/) will be used to message participants. This means that participants mobile numbers will be shared with eSendex via a secure data transfer in order to run the service, and all appropriate security steps are taken to ensure the confidentiality and protection of the data in their care. Participants have an optional consent to have there information held by essendex in order to be contacted via text message.

Any personal data will be held in a secure database using encryption, with restricted password protected access. Only appropriate members of the participating site team and NCTU research team will have access to these data.

Participant confidentiality will be further ensured by utilising identification code numbers to correspond to treatment data in computer files.

Data generated as a result of this trial will be available for inspection on request by the sponsor local R&D departments and the NCTU.

Anonymised participant data may be shared with researchers external to the trial research team in accordance with the NCTU's data sharing procedure. All requests for data should be sent to the NCTU.

